## Study Synopsis

SCIENTIFIC TITLE	Survey of Beliefs and Practices regarding the Donor Site Wound in Paediatric Split-Thickness Skin Grafts
SHORT TITLE	Paediatric Donor Site Wounds in Australasia
SPONSOR	Pegg Leditschke Children's Burns Centre
RATIONALE	No existing data demonstrating practices in the treatment of the donor site wound following paediatric split-thickness skin grafting.
PRIMARY AIM	Benchmark current practice regarding treatment of the DSW in children.
SECONDARY AIM	
 
1. To determine whether there are differences in practice, determined by 
 
• Geography (Australia vs New Zealand, state differences)
 
• Experience (years since Fellowship, practices of peers, number treated annually)
 
• Type of practice (paediatric only vs mixed adult and children)
 
 
 
2. To determine if there have been appreciable changes since a similar survey was done in Australia
 

PRIMARY ENDPOINT	Survey open for three months, with reminder emails at 2, 4 and 8 weeks
STUDY DESIGN	Online survey
STUDY DURATION	3 months
SAMPLE SIZE & POWER	Aim to have 100% coverage of inclusion criteria below
RECRUITMENT CENTRES	Direct invitation by Pegg Leditschke Children's Burns Centre
INCLUSION CRITERIA	
 
1. Consultant surgeon
 
2. Working in a burns unit
 
3. Treating children with burns
 
4. Creating donor site wounds for STSG
 
5. Working in Australia or New Zealand
 

DATA MANAGEMENT	Online survey, with option for paper-based responses. Data will be collected into a password protected electronic database (Survey Monkey).

## List of Abbreviations

AI	Associate Investigator
ANZCTR	Australia and New Zealand Clinical Trials Register
ANZ J Surg	Australia and New Zealand Journal of Surgery
CI	Chief Investigator
CHQ	Children's Health Queensland
DSW	Donor Site Wound
GCP	Good Clinical Practice
HREC	Human Research Ethics Committee
ICMJE	International Committee of Medical Journal Editors
NHMRC	National Health and Medical Research Council
PLCBC	Pegg Leditschke Children's Burns Centre
RCT	Randomised Controlled Trial
STSG	Split-Thickness Skin Graft

## Glossary of Terms & Definitions

Child	Birth to 16 th birthday
Adult	16 years and beyond

## 1.0 Introduction

### 1.1 Overview

The donor site wound (DSW) in paediatric split-thickness skin grafts (STSG) is an often-overlooked area of wound management; with most attention typically on the STSG itself rather than the iatrogenic DSW.

This survey seeks to determine the opinions and practices of burns surgeons in Australia and New Zealand, with respect to their treatment of the donor site wound in children as a consequence of skin grafting.

To some degree this has been done before, by Australasian Plastic Surgeon Patrick Lyall. [1] A similar survey, though with different questions, was carried out in the United Kingdom (UK) in 2012. [2]

Properties of an 'ideal' DSW dressing have been investigated at a world level by survey of practising clinicians. [3] While this survey had a small number of respondents only, most agreed an 'ideal' DSW dressing did not currently exist. Desirable qualities included lack of adhesion to the wound bed, pain-free dressing changes, absorbency, and ease of removal.

This study forms part of the PhD thesis of the primary investigator. It is part of a suite of publications in the field of paediatric donor site wounds. [4-7] The study is an electronic survey of Australasian Burns Surgeons practising in centres treating children with burns.

The **primary aim** is to:

Benchmark current practice regarding treatment of the DSW in children.

The **secondary aims** are:

3. To determine whether there are differences in practice, determined by
  - Geography (Australia vs New Zealand, state differences)
  - Experience (years since Fellowship, practices of peers, number treated annually)
  - Type of practice (paediatric only vs mixed adult and children)
4. To determine if there have been appreciable changes since a similar survey was done in Australia [1]

### 1.2 How is the DSW managed currently?

This information is not available, as there are no data on current DSW management. The majority of studies state alginates are the most common DSW, but with little supporting evidence to back this assertion. Local data from the PLCBC show that DSW management is often surgeon-specific. There were three DSW dressings in use prior to our recent randomised controlled trial (RCT). There were a number of factors determining which dressing was chosen – both surgeon-specific and patient-specific factors.

### 1.3 Why examine this?

Lack of current data regarding practice means centres may be operating in a vacuum, unaware of how their practice compares to that of other centres regionally.

## 2.0 Study Aims

### 2.1 Primary Aim

The **primary aim** is:

In children being treated for burns with split-thickness skin grafts, what are the beliefs and practices of their treating consultant surgeons with respect to the donor site wound, in Australia and New Zealand?

Our **primary hypothesis** is that the majority of surgeons

- will be using an alginate dressing
- will change it at 5-7 days
- will expect wound re-epithelialisation at 7-10 days
- will have differences of opinion regarding negative aspects of a DSW

The **secondary aims** are:

5. To determine whether there are differences in practice, determined by
  - Geography (Australia vs New Zealand, state differences)
  - Experience (years since Fellowship, practices of peers, number treated annually)
  - Type of practice (paediatric only vs mixed adult and children)
6. To determine if there have been appreciable changes since a similar survey was done in Australia [1]

Our **secondary hypotheses** are that: there will be differences between paediatric-only surgeons, and those with mixed practices; there will be definable geographic differences in practice; there will be definable experience differences in practice.

## 3.0 Study Design Overview

We plan an online cohort study of consultant burns surgeons in Australia and New Zealand performing STSGs in children and therefore creating a DSW that has to itself be treated.

### Experimental Design

- **Groups:**  
Consultant surgeons in Australia and New Zealand treating performing STSG in children with burns
- **Blinding:**  
None. Names will be collected to assist with coverage. Names will be removed from data prior to analysis.
- **Outcome data source/s:**  
Self-reported data from consultants taking part in the survey.
- **Data collection:**  
Electronic database (SurveyMonkey), with the availability for paper-based forms if requested. Data will be entered into a password-protected electronic database.
- **Study duration:**  
Testing of the form suggests it can be completed in under 10 minutes.  
The trial will run for three months to maximise the response rate.

## 4.0 Study Cohort

### 4.1 Number of participants/centres

There are a number of centres performing STSG in children, as outlined below

New Zealand: Middlemore Hospital, South Auckland  
Waikato Hospital, Hamilton  
Hutt Hospital, Upper Hutt  
Christchurch Hospital, Christchurch

Australia: Queensland Children's Hospital, Brisbane  
Gold Coast University Hospital, Gold Coast  
Townsville Base Hospital, Townsville

Fiona Stanley, Perth

Sydney Children's Hospital, Randwick  
Westmead Children's Hospital, Westmead

Royal Children's Hospital, Parkville  
Monash Children's Hospital, Clayton

Royal Hobart Hospital, Hobart

All consultant surgeons performing STSG in children with burns in these centres will be eligible to participate in the study.

### 4.2 Recruitment plan

Only participants who fulfil inclusion criteria will be eligible for approach. Data regarding consultants in these centres are readily available publically. The CI will directly approach the lead consultant in each centre to explain the trial and confirm the names of eligible consultant staff. An individual email invitation will then be sent to each consultant. This email will explain the trial and provide a link to the online survey. It will include a return email invitation to address any concerns or questions that may be raised regarding the survey.

Follow up emails and/or phone calls will be sent at 2, 4 and 8 weeks from the time the study opens. The survey will include an option to take no further part in it as an initial question. The name of the consultant will also be requested, in order to not continue to approach those consultants who do not wish to be included in the survey.

### 4.3 Inclusion criteria for enrolment

1. Consultant surgeon
2. Performing STSG on children for burns
3. Working in Australia or New Zealand
4. Working in a recognised Burns Unit

### 4.4 Exit criteria during the study

Consent withdrawal. If this occurs and the investigators are notified, the data pertaining to that individual will be deleted from the database and the participant notified that this has occurred.

## 5.0 Study Implementation

### 5.1 Study sites

Study will be conducted online, with the central database being administered from the PLCBC at QCH.

### 5.2 Number of participants

It is estimated there are 60-70 consultant surgeons performing STSG in children in Australia and New Zealand.

### 5.3 Estimated duration of study

Three months for data collection. A further three months for analysis and writeup.

### 5.4 Ethics and regulatory approvals

The study will be conducted according to Good Clinical Practice (GCP), and the Declaration of Helsinki.

The study protocol, data collection forms (including consent and information statements), and other documents required for ethical approval will be submitted to the Children’s Health Queensland Human Research Ethics Committee (CHQ HREC) for approval prior to study commencement.

### 5.5 Informed consent

Informed consent processes are to be consistent with the principles of GCP, the Declaration of Helsinki, NHMRC requirements and cultural aspects of consent in Indigenous communities. Freely given informed consent will be obtained from each participant prior to enrolment. A copy of the study protocol will be made available as a part of the invitation email. Entry into the study will be deemed as consent. A sentence to the effect that declining to participate is acceptable will be included in the invitation email. A contact email for questions will be provided.

No inducements, monetary or otherwise, will be provided to encourage participation in the survey.

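### The invitation offers every surgeon the full protocol, which prints three of the answers the survey sets out to collect, so the benchmark is exposed to an avoidable risk of anchoring

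*Protocol*

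**What the plan says.** Section 4.2 (Recruitment plan) sets out the approach to participants: "An individual email invitation will then be sent to each consultant". It adds: "This email will explain the trial and provide a link to the online survey". Section 5.5 (Informed consent) attaches the protocol to that message: "A copy of the study protocol will be made available as a part of the invitation email". The same section says: "Entry into the study will be deemed as consent". The protocol is therefore on offer before the survey is opened, as part of the material on which consent rests.

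Section 2.1 (Primary Aim) states the primary hypothesis in the form of answers. It "is that the majority of surgeons" will behave in four listed ways. Three of the four name a specific answer: "will be using an alginate dressing", a dressing change at 5-7 days, and "will expect wound re-epithelialisation at 7-10 days". The fourth expects opinions on the drawbacks of the donor site wound to differ, and points to no particular answer.

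Section 3.0 (Experimental Design) makes self-report the only source of outcome data, with no blinding, and says: "Names will be collected to assist with coverage". Names are removed before analysis.

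**The concern.** The survey exists to find out what surgeons do and believe, because section 1.3 says centres do not know how their practice compares with that of others. Yet the invitation offers each surgeon a statement of the presumed norm before the questions are answered. A printed day range is an easy anchor for someone recalling or estimating an interval, and a named product tells the reader what colleagues are thought to use.

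What is at stake is the primary benchmark: the share using each dressing and the distribution of the two time intervals. The second secondary aim is also touched. If some answers move towards the printed ones, a difference from the earlier Australian survey, or the lack of one, could be misread. Because all invitees are offered the same material, the design contains no group known to be unexposed, so no later analysis could reliably correct a shift. The matter has to be settled before invitations go out, and it is not something an analysis plan could resolve.

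**Working it through.** The protocol gives no figure for this point, so there is none to reproduce. The check has two parts.

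**The text, side by side**

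1. Who is offered the protocol: each eligible consultant, individually (sections 4.2 and 5.5).
2. When: in the email that contains the survey link, so before answering (sections 4.2 and 5.5).
3. What it contains: three specific expected answers (section 2.1). Section 1.2 also reports that most studies call alginates the commonest choice, but says in the same sentence that the evidence for this is slight.
4. How outcomes are measured: unblinded self-report, with names collected (section 3.0).
5. Safeguards: the protocol text provides for no copy without the hypotheses, no delay in releasing them, and no record of who read them.
6. Whether consent needs the full protocol: section 5.4 lists information statements separately from the protocol among the ethics documents, so another vehicle already exists.

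**An illustration of size**

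Inputs: the eligible population of 60-70 is from sections 5.2 and 7.2. The true share t and the switching proportion s are assumptions; the document gives neither.

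If a proportion s of those who would not otherwise give the printed answer move to it, then

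observed share = t + (1 − t) × s.

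- t = 0.45, s = 0.10: 0.45 + 0.55 × 0.10 = 0.505
- t = 0.48, s = 0.05: 0.48 + 0.52 × 0.05 = 0.506
- t = 0.40, s = 0.20: 0.40 + 0.60 × 0.20 = 0.520
- t = 0.65, s = 0.10: 0.65 + 0.35 × 0.10 = 0.685 (a majority either way)
- t = 0.25, s = 0.20: 0.25 + 0.75 × 0.20 = 0.400 (a minority either way)

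The first three cases cross 50%. The last two do not, but the reported percentage still moves by 3.5 and 15 points.

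The smallest s that brings the expected share to 50% is (0.5 − t)/(1 − t): 0.05/0.55 = 9.1% at t = 0.45, and 0.10/0.60 = 16.7% at t = 0.40.

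In head counts with full response, a majority needs 31 of 60 or 36 of 70. At t = 0.45 the expected counts are 27 and 31.5, so about 4 to 5 surgeons moving would create one. At t = 0.40 they are 24 and 28, so 7 to 8 would be needed.

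Treating respondents as independent draws with t = 0.45, the binomial chance of observing a majority for N = 60, 65 and 70 is 0.17-0.21 with no switching, 0.48-0.53 with s = 0.10, and 0.79-0.84 with s = 0.20.

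**The case against.** A reader might infer that every respondent will be primed, that the bias must run towards the hypothesis, and that a majority finding would therefore be worthless. The documents do not support that, for these reasons:

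- **Exposure is offered, not imposed.** The protocol is made available; nobody has to open it. Section 3.0 describes a form that takes under 10 minutes, and many may go straight to the link. This stands.
- **Direction is not established.** Nothing presents the printed answers as good practice; they are predictions about peers. A wish to appear distinctive could push the other way. This stands.
- **Section 1.2 doubts the alginate claim** and describes dressing choice at the sponsor's centre as often specific to the surgeon. That may weaken the cue. This stands, although section 2.1 then predicts alginate without qualification.
- **Two of the three items are the surgeon's own routine practice,** which should be harder to move than a belief such as expected healing time. This is reasonable, and it limits the likely effect on product choice.
- **The majority-crossing figures depend on shares assumed just under 50%.** This is correct. Moreover, the protocol states no test against 50%, and its headline aim is to benchmark practice.
- **The questionnaire is not shown,** so wording and answer categories, which affect anchoring, cannot be judged. That the survey asks about these items is an inference from the primary aim, though a safe one.
- **The remedy may be incomplete.** Section 9.0 makes registration a milestone before the start, so the hypotheses may be findable. This makes the fix partial, but not useless: a registry entry has to be looked up, whereas the protocol comes with the invitation.

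These points limit the strength of the conclusion. They do not alter the fact that the expected answers are offered ahead of the questions with no safeguard and no evident need.

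**Conclusion.** The point holds as a design risk of moderate severity. The protocol offers three of its expected answers to each invitee before they respond, on outcomes that are unblinded and self-reported. Respondents who read them may be anchored.

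The size of the effect is unknown, and so are its direction and the number of readers. The illustration shows only that a small movement could matter: with a true share of 45%, about 4 to 5 surgeons of 60-70 would be enough to turn a minority into a majority. That result rests on assumed shares and switching rates, on full response, and on movement in one direction. With a share well away from 50% the majority verdict would not change, but the benchmark percentage could still be off by several points.

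It would go too far to say that the outcomes are primed or that the hypothesis is bound to be confirmed.

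**What to change.** In section 5.5, replace the sentence that makes the protocol available with text such as: *A participant information statement that omits the hypotheses and expected answers accompanies the invitation. The full protocol is provided after the survey closes.* If the ethics committee wants a protocol available earlier, supply a copy without the section 2.1 hypotheses and the section 1.2 sentence on alginates.

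If the full protocol must stay with the invitation, a weaker fallback is to add one item asking whether the respondent read it before answering, and to report the exposure as a limitation. The resulting comparison would be self-selected, so it would inform the reader without correcting the estimate.

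The cost is small. One sentence of section 5.5 changes, and the consent material under ethics review changes slightly. Invitees see the hypotheses later than they otherwise would. The protection is only partial if the registry entry shows the hypotheses.

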### 5.6 Participant identification numbers

Participants will be assigned a consecutive number upon entry into the survey. Names will be redacted from information prior to transfer to statistical analysis software. A master file will be kept to allow re-identification if clarification of any answer is required.

### 5.7 Outline of study procedures

	0 weeks	2 weeks	4 weeks	8 weeks
Initial email invitation				
Reminder email invitations				

### 5.8 Study completion

The database will be closed to online entry at 3 months. Any missing data will be located and approaches made to individual surgeons requesting completion of these data.

## 6.0 Safety Evaluation and Adverse Effects

### 6.1 Adverse effects

This is an online survey of practice. No adverse effects are anticipated. No patients are directly involved in this study.

## 7.0 Data Management and Analysis

### 7.1 Data management

Data will be entered into SurveyMonkey, either by participants online or by transcription of any paper-based forms submitted to the study investigators.

### 7.2 Sample size

There are approximately 60-70 consultant surgeons eligible to participate in this survey. The community of practice in this field is small, and this is an area of interest and discussion among surgeons. We hope this will encourage near universal uptake of the survey

### 7.3 Data analyses

A detailed data analysis plan will be prepared prior to analysis. Data will be audited, cleaned and locked prior to final analysis. Names will be deleted and data analysed in aggregate only.

Subgroup analyses, as per the secondary outcomes of interest, will include the following co-variables:

- Geography (Australia vs New Zealand, state differences)
- Experience (years since Fellowship, practices of peers, number treated annually)
- Type of practice (paediatric only vs mixed adult and children)

It is unlikely data will be normally distributed, therefore non-parametric analyses will be used. Tests will be two-tailed, and a p value of 0.05 will be deemed significant.

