## 10.9 Confidentiality

All identifiable information on study participants will be retained in password protected files and locked cabinets or locked rooms at the study site. Access to this information will only be provided to immediate study staff, unless required by legislative or regulatory agencies and the HREC. Consent to participate in this study will include consent for access to data by such agencies.

No identifying information will be included in study reports:

- Names will be removed and participant numbers assigned
- Geographic data will be replaced with an assigned number for each state, and for New Zealand.

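### Surgeon-level tests of country and state ignore the 13 units: they reject too often if practice is shared within units, and two states consist of a single unit

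*Protocol*

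**What the plan says.** Section 7.3 fixes three things: the comparisons, the family of tests and the threshold. Geography is one of the listed factors ("Geography (Australia vs New Zealand, state differences"). On method it says: "It is unlikely data will be normally distributed, therefore non-parametric analyses will be used". On the threshold: "Tests will be two-tailed, and a p value of 0.05 will be deemed significant". Section 2.1 makes geographic differences a secondary hypothesis.

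Recruitment is by whole unit. Section 4.1 lists the centres and adds: "All consultant surgeons performing STSG in children with burns in these centres will be eligible to participate in the study". Section 7.2 gives the head count: "There are approximately 60-70 consultant surgeons eligible to participate in this survey".

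The protocol does not name the unit as a factor in any analysis. Section 7.3 does promise a detailed analysis plan before analysis; that plan is not at hand.

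**The concern.** Every surgeon in a unit has the same country and the same state. Any similarity among colleagues therefore goes straight into the contrast between countries or between states. The usual rank and contingency-table tests take each surgeon as an independent observation. With about five surgeons per unit, they would credit the comparison with more information than it has.

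The protocol itself gives reason to expect some similarity. It lists peers' practice among the possible determinants (Sections 2.1 and 7.3), and Section 1.3 speaks of a centre's practice as something to set against that of other centres. What is at stake is the geographic secondary hypothesis: ordinary variation from unit to unit could be reported as a difference between countries or states.

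**Working it through.** **Inputs from the protocol**
- Surgeons: 60-70 (Sections 5.2 and 7.2); midpoint 65.
- Units: 13 by count of the Section 4.1 list. New Zealand has 4. Australia has 9: Queensland 3, New South Wales 2, Victoria 2, Western Australia 1, Tasmania 1 (states read from the place names).
- Surgeons per unit: 60/13 = 4.6 to 70/13 = 5.4. Unit sizes are not given.
- Threshold: 0.05, two-sided, per test (Section 7.3).

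**Assumption.** The protocol gives no ICC, so a range of 0 to 0.5 is shown.

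**Baseline.** The protocol has no power calculation to reproduce. The check is that ordinary tests hold their level when ICC = 0. In simulation they do: 4.4% for Mann-Whitney, 2.6% for Fisher's exact test and 4.2% for Kruskal-Wallis across states.

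**Formula for country**
- Design effect: DE = 1 + (m - 1) x ICC, with m = 65/13 = 5.
- Effective number of surgeons: 65/DE.
- Actual two-sided error: 2 x [1 - Phi(1.96/sqrt(DE))].
- Example at ICC 0.3: DE = 1 + 4 x 0.3 = 2.2; 65/2.2 = 29.5; 1.96/sqrt(2.2) = 1.32; error 18.6%. It is 17.5% with 60 surgeons and 19.8% with 70.

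**Simulation.** No true difference, 13 units of about five surgeons, 3000-4000 runs per setting. Fisher and chi-square use a yes/no answer at 50%. Mann-Whitney and Kruskal-Wallis use a five-level answer, with the ICC set on its underlying scale. Five states means the nine Australian units; six regions means those states plus New Zealand. A range in a cell is the spread over separate runs. Simulation error is about 0.4 percentage points near 5% and up to about 1 point at the higher rates.

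| ICC | DE | Effective n | Country, formula | Country, Fisher | Country, chi-square | Country, Mann-Whitney | Five states, Kruskal-Wallis | Six regions, chi-square |
|---|---|---|---|---|---|---|---|---|
| 0.05 | 1.2 | 54 | 7.4% | 4.4% | not run | 7.0% | 7.6% | 9% |
| 0.1 | 1.4 | 46 | 9.8% | 6.5-7.6% | 9.9-10.8% | 10.5% | 12.8% | 15-17% |
| 0.3 | 2.2 | 30 | 18.6% | 16% | 19-21% | 17.8% | 34.7% | 47-48% |
| 0.5 | 3.0 | 22 | 25.8% | 23-24% | 27-29% | 26.2% | 58.4% | 70-71% |

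One assumed set of unequal unit sizes raises the Mann-Whitney rate for country to 22% at ICC 0.3 and 32% at 0.5.

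**Unit-level analysis.** Mann-Whitney on the 13 unit means, 4 against 9, rejects in about 3-5% of runs at every ICC from 0 to 0.5. A permutation test has 13!/(4! x 9!) = 715 ways to assign the New Zealand label to 4 of 13 units, enough for a test at 0.05.

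**Single-unit states.** With one listed unit in Western Australia and one in Tasmania, state and unit are the same variable there. This needs no ICC.

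**The case against.** The strongest objection is that the protocol names no test and nowhere says that surgeons will be treated as independent. It defers detail to a later plan, and unit-level permutation is itself non-parametric, so Section 7.3 does not rule out a sound analysis. All of that is true, and a missing clustering method alone would not be a finding. But Section 7.3 already fixes the geographic comparisons, the test family and the threshold without using the unit, and an ordinary reading leads to surgeon-level tests.

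Second, the ICC is assumed. Section 1.2 reports that management in the sponsor's own unit tends to differ by surgeon, with three dressings in use, which points to a low value there. This stands as a limit on size: at ICC 0.05 an exact test of country is not inflated (4.4%).

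Third, coverage is meant to be near complete, and p values mean less in a census. That is fair, but the protocol plans p values, and the argument supports describing states without them.

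A reader might infer three stronger points that the documents do not support:
- **That practice-type tests will also reject too often.** Section 2.1 attaches this factor ("Type of practice (paediatric only vs mixed adult and children") to the surgeon, and nothing says it is constant within a unit. If types are evenly mixed within units, the ordinary test becomes conservative: 4% at ICC 0.1, 2.5% at 0.3 and 1.1% at 0.5. Only if type is constant within units (5 against 8 units assumed) does it inflate, to 9% at ICC 0.1 and 18% at 0.3.
- **That the peers item simply is the within-unit correlation.** The questionnaire is not shown, and peers are not defined as colleagues in the same unit.
- **That the confidentiality rule removes the unit code.** Section 10.9 says "Geographic data will be replaced with an assigned number for each state, and for New Zealand", but this governs study reports. Section 5.6 keeps a master file for re-identification, so the unit can be recovered.

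**Conclusion.** The point holds for geography, conditionally. If practice is correlated within units, surgeon-level tests of country reject in about 4-7% of cases at ICC 0.05, 7-11% at 0.1 and 16-21% at 0.3, against a nominal 5%. Tests of states or regions reject in about 8-9%, 13-17% and 35-48%, depending on test and grouping. These figures assume 13 units of about five surgeons, and an ICC that the documents neither give nor settle.

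One part is unconditional: for Western Australia and Tasmania, a state difference cannot be separated from the practice of the one listed unit.

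The tests concerned serve secondary aims; the primary aim is descriptive and is not touched. The change is worth making because a named hypothesis could otherwise be declared confirmed on unit-to-unit variation alone.

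**What to change.** Before analysis, write into the analysis plan:
1. Carry a coded unit identifier into the analysis file, taken from the Section 5.6 master file, and keep it out of reports so that Section 10.9 is respected.
2. Test Australia against New Zealand by permuting country labels across the 13 units (715 arrangements), or by another unit-level test such as Mann-Whitney on unit means.
3. Report state differences descriptively, without p values, and say which states rest on one unit.
4. For practice type, use a unit-stratified test (van Elteren or Cochran-Mantel-Haenszel) if type varies within units, and a unit-level test if it does not.

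The cost is one column and a few sentences. The real downside is less power and wider intervals for country, since the comparison then rests on 4 units against 9.
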